### 12.2 Temporary suspension of all study drug administration in all study participants

The following events will trigger a temporary suspension of all study drug administration:

- Development of a grade 4 adverse event that is related to the study medication
- At least two participants experience sustained antiretroviral treatment failure that is not attributable to non-adherence with antiretroviral medications. Sustained HIV rebound is defined as HIV RNA levels >400 copies/mL for longer than a 4-week period.
- At least two participants experience a significant and sustained CD4 T cell count decline that is not attributable to non-adherence with antiretroviral medications. A significant and sustained CD4 T cell count decline is defined as two measurements taken at least two weeks apart of either a) CD4 T cell counts that are <50% of the baseline relative CD4 T cell count (average of screening and pre-entry values) or b) CD4 T cell counts <200/mm^3.

The SMC will review these events to determine if any study procedures should be changed. After this review, the SMC may allow the study to continue. A quorum of three Committee members is required for the review of the event(s) and for providing recommendation. The FDA will be informed in the event that temporary suspension of study medication occurs.

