## Protocol

The committee will meet by conference call every month during the trial or at an appropriate interval based on the pace of enrollment. A **quorum** of **three** Committee members is required for each scheduled meeting, teleconference or unscheduled meeting. A project manager will be responsible for tabulating all adverse events, distributing these tables to the members of the Internal Safety Review Committee and organizing the meetings.

The committee will review all adverse events that occur during the trial. The Internal Safety Review Committee will be responsible for forwarding the following reports to the Safety Monitoring Committee for immediate review:

- a. Serious adverse events.
- b. Grade 3 and 4 adverse events that are related to the study medication.
- c. CD4 T cell count decline to <50% of relative CD4 cell count compared to baseline (average of the screening and pre-entry visits) that is not attributable to non-adherence with antiretroviral medication.

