### 10.8 Contraindications to further administration of study drugs

Clinical events listed below constitute absolute **contraindications to further administration** of the study medication; if any of these events occur during the study, the participant must not receive additional doses of the investigational product but may continue other study procedures at the discretion of the investigators. The participant must be followed until resolution of the event, as with any adverse event.

- Early or delayed hypersensitivity reactions
- Pregnancy

The following adverse events constitute **contraindications to administration** of the study medication **at that point in time**; if any one of these adverse events occurs at the time scheduled for administration of the study drugs, administration of study drugs will be delayed for a maximum of one week or withdrawn from study participation at the discretion of the investigators. The participant must be followed until resolution of the event, as with any adverse event (see Section 10.7).

- Acute disease, defined as the presence of a moderate or severe illness with or without fever. However, study medication can be administered to persons with a minor illness such as diarrhea, mild upper respiratory infection with or without low-grade febrile illness, i.e. oral temperature < 100.5F.
- Oral temperature of  $\geq 100.5F$

### 10.9 Criteria for Study Continuation to stage 2 and 3

After completion of stage 1, all safety data will be reviewed by the internal safety review committee (ISRC), the external safety monitoring committee, the IRB and the FDA. The study can only proceed to stage 2 if all of these committees agree that the safety profile in stage 1 is acceptable. A similar interim review will occur after completion of stage 2 to determine study progression to stage 3.

Dose escalation criteria are defined as:

- a) No more than one subject has experienced a  $\geq$  Grade 3 toxicity event that is related to study treatment (as judged by the investigators) prior to or on Day 28 after the treatment administration; however, if

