## Protocol

grade 3 toxicity events are limited to clinically insignificant laboratory abnormalities, the independent SMC may, after a detailed review of all safety events, allow progression of the study to the next stage.

- b) None of the subjects have experienced a serious or worse AE or toxicity that is Grade  $\geq 4$  and related to study treatment (as judged by the investigators) prior to or on Day 28 after the treatment administration.
- c) No patient has experienced a cardiac ischemic event or shown ECG evidence of myocardial ischemia during the study treatment.

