### 12.3 Permanent suspension of all study medication in all study participants

After review and confirmation by the SMC, permanent suspension of all study medications will be considered if:

- Two or more participants who received study medication develop any grade 4 adverse event that is related to the study medication.
- Two or more participants experience sustained antiretroviral treatment failure not attributable to non-adherence with antiretroviral medication.
- Two or more participants experience a significant and sustained CD4 T cell count decline that is not attributable to non-adherence with antiretroviral medications.
- At the request of the pharmaceutical companies providing the investigational agents (Novartis AG and Roche AG).

The SMC will review the event to determine if any study procedures should be changed. After this review, the SMC may allow the study to continue. A quorum of three Committee members is required for evaluation of the event(s) and for providing recommendation. The final decision for study suspension remains with the Sponsor. The FDA will also be informed in the event that permanent suspension of study medication occurs.

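### Cardiac ischemia short of a related grade 4 event bars escalation (10.9) but does not pause dosing of other participants at the same dose: a cheap improvement to 12.2

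*Combined protocol and SAP*

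**What the plan says.** **Holds on dosing for everyone.** Section 12.2 opens with "The following events will trigger a temporary suspension of all study drug administration" and lists three events. One is an adverse event: "Development of a grade 4 adverse event that is related to the study medication". The other two are sustained antiretroviral failure and sustained CD4 decline, each in at least two participants. Section 12.3 is discretionary: after SMC review, "permanent suspension of all study medications will be considered if" one of its conditions is met. Its adverse-event condition is two or more participants with related grade 4 events.

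**Bars to escalation.** Section 10.9(c) requires that "No patient has experienced a cardiac ischemic event or shown ECG evidence of myocardial ischemia during the study treatment". It sets no condition on grade or relatedness. Section 10.9(a) limits related toxicity of grade 3 or higher to one participant, with an SMC allowance where "grade 3 toxicity events are limited to clinically insignificant laboratory abnormalities". These criteria apply after stage 1, and "A similar interim review will occur after completion of stage 2 to determine study progression to stage 3". No such review follows stage 3.

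**Other oversight.**
- 10.1: the Internal Safety Review Committee (ISRC) reviews all adverse events and forwards serious events and related grade 3/4 events to the SMC for immediate review. On its own meetings: "The committee will meet by conference call every month during the trial or at an appropriate interval", depending on the pace of enrollment.
- 10.2: the SMC has two scheduled meetings a year, plus unscheduled meetings for serious events or grade 4 events attributed to study drug.
- 10.5.6: serious events are reported within 24 hours, including to the SMC.
- 11.3: a related grade 3 or 4 event stops dosing in that participant.
- 12.1.2: the SMC, NIAID, the FDA or the suppliers can terminate the study.

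**The concern.** The protocol treats ischemia as a risk worth planning for. Section 5.3.5 reports it with panobinostat, 7.1.17 requires a negative cardiac work-up, and under 10.9(c) a single event stops the move to the next dose. Yet that event need not delay the next participant at the dose at which it occurred. Followed to the letter, the plan allows others to start or continue, including at 15 mg, before the SMC has looked at it. A course runs from day 0 to day 4, so a review on a monthly or half-yearly calendar could come after several further courses.

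A hold protects only people not yet dosed or still in their course. It does nothing for the affected participant if ischemia first appears on the day 4 ECG, taken after the last dose.

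**Working it through.** **1. The rules side by side**

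| Ischemic event | Bars escalation (10.9) | Automatic hold for all (12.2) | Immediate SMC review (10.1) |
|---|---|---|---|
| Grade 4 and related | yes | yes | yes |
| Serious, but not both grade 4 and related | yes | no | yes |
| Non-serious, grade 3, related | yes | no | yes |
| Non-serious, and below grade 3 or judged unrelated | yes | no | not required |

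After stage 3 the second column has no effect, because there is no further dose level. In the last row 10.2 does not call an unscheduled SMC meeting either. Section 11.4.4 asks for local standard of care and cardiology referral if indicated, and mentions no hold.

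**2. The plan's own figures**

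Tables 7 and 8 in 14.3 are exact binomial tails, and all 24 entries reproduce. For N=18 and a 10% rate:
- at least one: 1 − 0.9^18 = 0.850 (stated 0.85)
- at least two: 1 − 0.9^18 − 18 × 0.1 × 0.9^17 = 0.550 (stated 0.55)

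**3. Ischemia in stage 3, for illustration**

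Inputs:
- Stage 3 participants given panobinostat: 4 (Arm A) + 10 (Arm B) = 14.
- Rates in 5.3.5: 12/666 = 1.8% (single agent, any causality) and 4% (combination regimen, against 1% in the control arm). Both come from oncology use.
- Assumed lower rates, with no source in the documents: 0.2% and 0.5%.
- Assumption: one-at-a-time dosing, which leaves the most people undosed. The documents give no enrollment pace.

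Formulas, for rate r:
- P(at least one of 14) = 1 − (1 − r)^14
- Expected number undosed after a first event, U = Σ over k = 0..13 of (13 − k) r (1 − r)^k
- The same given that an event occurs = U / [1 − (1 − r)^14]
- Expected further events among those undosed = r × U

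| r | P(at least one) | Undosed, given an event | Undosed, unconditional (U) | Further events (r × U) |
|---|---|---|---|---|
| 0.2% | 2.8% | 6.5 | 0.18 | 0.0004 |
| 0.5% | 6.8% | 6.6 | 0.45 | 0.002 |
| 1.8% | 22.5% | 6.8 | 1.5 | 0.03 |
| 4% | 43.5% | 7.2 | 3.1 | 0.12 |

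Given an event, the number undosed can lie anywhere from 0 to 13. Overlapping dosing lowers it.

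**4. A second participant with related grade 3 or higher toxicity**

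The documents give no rate for this regimen. In CLEAR (5.4.3.1), 0 of 15 participants had a related event above grade 1, so the one-sided 95% upper limit is 1 − 0.05^(1/15) = 18%. CLEAR used no interferon, so this does not bound Arm B. P(at least two of 18) at rates of 0, 1%, 5%, 10% and 18% is 0, 0.01, 0.23, 0.55 and 0.86. That range is too wide to say how often such a trigger would be met.

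**The case against.** **Different rules answer different questions.** Moving to a higher dose can reasonably need a stricter standard than continuing a dose already in use, and the protocol grades its responses: individual stop, group hold, permanent suspension. This stands. A reader might infer that 10.9 and 12.2 contradict each other, but nothing in the documents requires the two lists to match.

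**Ischemia is not left unattended.** A reader might infer that ischemia never triggers a hold or goes unreviewed. Neither is so. A related grade 4 ischemic event triggers 12.2. Serious ischemia reaches the SMC within 24 hours and is reviewed at once, as are related grade 3 events. The ISRC sees every adverse event and can meet more often than monthly. All dosing takes place in one unit, so the investigators can pause on their own initiative. This narrows the gap but does not close it, because none of these provisions requires a hold while the review takes place.

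**The numbers are weak.** The sourced rates come from cancer patients; here participants have a cardiac work-up, cardiac disease is excluded and panobinostat is given three times. The figure of about 7 undosed depends on an event having occurred and on one-at-a-time dosing. Unconditionally the expected number of further ischemic events is at most about 0.12 at the rates shown, and a hold would avert them only if dosing did not resume. This also stands: the case rests on the rule and its low cost, not on a forecast.

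**A broad trigger could do harm.** Section 5.3.5 says that asymptomatic T-wave abnormalities are frequent with panobinostat. Read loosely, they could stop all dosing, and an event in Arm C would say nothing about panobinostat. A hold could also break an every-other-day course when the day 10 comparison rests on 9, 3 and 3 evaluable participants (14.3). This stands, and it shapes the fix.

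**Conclusion.** The point holds as a cheap improvement to a safety rule. For cardiac ischemia that is not both grade 4 and judged related, nothing requires a pause in dosing other participants at the same dose within any stage. Stage 3 matters most: 14 participants on the highest dose, with no later escalation review. For serious or related grade 3/4 ischemia, only the hold during review is missing. For non-serious ischemia that is below grade 3 or judged unrelated, prompt SMC review is not required either.

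The textual finding needs no assumption; its size does. The 22% and 44% are illustrations at oncology rates, neither estimates for this population nor a ceiling, and the 3% and 7% rest on rates with no source in the documents.

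A reader might extend the point to a second participant with related grade 3 or higher toxicity, which also bars escalation ("No more than one subject has experienced a" such event, in 10.9(a)) without a group hold. The documents do not support giving that equal weight: those events already go to the SMC for immediate review, the affected participant normally stops dosing, and no event rate is available. A hold there is a design option.

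**What to change.** **Section 12.2, for every stage including stage 3.** Add a temporary suspension of panobinostat dosing, pending SMC review, when a participant who has received panobinostat has either:
- a cardiac ischemic event, or
- ECG evidence of myocardial ischemia confirmed by the protocol cardiologist already named in 7.1.17. State that non-specific T-wave changes do not count.

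The SMC would lift the hold through the existing 12.2 process.

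**Section 10.2.** Add the same event to the reasons for an unscheduled SMC meeting.

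**Optional.** A hold for a second participant in a stage with related grade 3 or higher toxicity, keeping the 10.9(a) laboratory allowance. Writing grade 4 or higher in 12.2 is tidying only.

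**Cost.** A few lines of text, with no change to sample size, endpoints or analysis. If the trigger is met, there is a short, reversible pause and an extra call of the three-member SMC. Anyone between day 0 and day 4 may have the course interrupted, which matters slightly for the small day 10 comparison. Because randomization takes place on day 0 just before dosing (7.5), new randomizations would in practice wait too. If ischemia is rare, the rule will seldom be used.

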### 12.3 Permanent suspension of all study medication in all study participants

After review and confirmation by the SMC, permanent suspension of all study medications will be considered if:

- Two or more participants who received study medication develop any grade 4 adverse event that is related to the study medication.
- Two or more participants experience sustained antiretroviral treatment failure not attributable to non-adherence with antiretroviral medication.
- Two or more participants experience a significant and sustained CD4 T cell count decline that is not attributable to non-adherence with antiretroviral medications.
- At the request of the pharmaceutical companies providing the investigational agents (Novartis AG and Roche AG).

The SMC will review the event to determine if any study procedures should be changed. After this review, the SMC may allow the study to continue. A quorum of three Committee members is required for evaluation of the event(s) and for providing recommendation. The final decision for study suspension remains with the Sponsor. The FDA will also be informed in the event that permanent suspension of study medication occurs.

## 13.0 SAMPLE HANDLING AND ANALYSIS

### 13.1 Treatment and Storage of biological samples

Whole blood and serum will be collected in standard collection tubes containing EDTA or Heparin as anticoagulant. PBMC for virological and immunological assays will be extracted by Ficoll density centrifugation and cryopreserved according to standard procedures.

## Protocol

### 13.2 Standard laboratory assays

The following measurements will be performed when indicated in Table 1.

#### 13.2.1 Virology

Screening HIV-1 RNA tests must be performed using the Roche Taqman version 2.0 assay by a laboratory that possesses CLIA certification or its equivalent. Eligibility will be determined based on the screening value.

#### 13.2.2 Chemistry

Sodium, potassium, chloride, BUN,  $\text{HCO}_3^-$ , creatinine, ALT (SGPT), AST (SGOT), and total bilirubin will be measured in the clinical laboratory of the Massachusetts General Hospital according to standard procedures.

#### 13.2.3 Hematology

Hemoglobin, mean corpuscular volume (MCV), white blood cell count (WBC), differential WBC, platelet count, partial thromboplastin time, prothrombin time will be measured in the clinical laboratory of the Massachusetts General Hospital according to standard procedures.

#### 13.2.4 Other laboratory studies

TSH, HBsAg, HBV DNA PCR, HCV Ab and HCV RNA PCR will be done at the local clinical laboratories of MGH.

### 13.3 Virologic assays for HIV-1 reservoir quantification

The following virological assays will be performed for measuring effects of the study medication on size of the viral reservoir.

#### 13.3.1 CD4 T cell-associated HIV-1 RNA

Unspliced HIV-1 RNA in isolated CD4 T cells will be measured using established protocols to determine the influence of the study medication on HIV-1 RNA transcription.

#### 13.3.2 Proviral HIV-DNA in CD4 T cells

Proviral HIV-1 DNA will be analyzed in isolated total CD4 T cells, using optimized protocols for quantitative analysis of HIV-1 DNA. Analysis of proviral HIV-1 DNA in sorted naive, central-memory, effector-memory, terminally-differentiated CD4 T cells and CD4 T memory stem cells will be performed if sufficient PBMC are available.

#### 13.3.3 Analysis of integrated HIV-1 DNA and HIV-1 2-LTR circles.

If sufficient PBMC are available, chromosomally integrated HIV-1 DNA and viral 2-LTR circles will be analyzed using DNA extracted from CD4 T cells, according to established experimental protocols.

#### 13.3.4 HIV Reactivation Assay

This assay is performed to assess changes in the functional HIV-1 reservoir after study treatment. The majority of the proviral HIV DNA sequences is defective virus not capable of completing replication cycles and therefore not able to drive viral rebound in the absence of cART. The HIV reactivation assay measures changes in the frequency of cells latently infected with replication competent virus, i.e. integrated HIV DNA capable of resuming viral replication once reactivated. As an alternative to HIV reactivation assays, the TILDA assay or full-genome HIV-1 sequencing assays will be considered.

## Protocol

### 13.3.5 Residual HIV-1 plasma RNA

Residual plasma viremia will be determined by single-copy assay (SCA). This assay is a real-time PCR-based method that can accurately quantify far lower levels of viremia than currently available commercial assays.

### 13.3.6 Phylogenetic studies

Cell-associated and plasma HIV-1 RNA and cell-associated HIV-1 DNA will be subjected to viral sequencing studies to investigate phylogenetic associations between reactivated virus in CD4 T cells, plasma viral sequences and proviral HIV-1 DNA in total CD4 T cells and specific CD4 T cell subsets.

## 13.4 Immunologic Assays

### 13.4.1 Immune phenotyping

Phenotypic characteristics of different leukocellular subsets during treatment with study medication will be analyzed using standardized flow cytometry or cytometry-by-time-of-flight assays (CyTOF). Activation, maturation and differentiation markers of CD4 and CD8 T cells, B cells, NK cells, regulatory T cells, myeloid and plasmacytoid dendritic cells will be analyzed.

### 13.4.2 Functional immunologic assays

The functional assays described below will be considered:

#### 13.4.2.1 Cytokine secretion assays

Cytokine in CD4, CD8 T cells and NK cells will be measured using intracellular cytokine staining protocols, followed by flow cytometric/CyTOF analysis.

#### 13.4.2.2 Cytotoxicity assays

Cytotoxic activities of NK cells and cytotoxic T cells will be analyzed by flow cytometry- or CyTOF-based intracellular quantification of cytotoxic granules, and/or by cellular degranulation assays.

#### 13.4.2.3 Proliferation assays

Proliferative activities of HIV-1-specific CD8 T cells will be analyzed after CFSE staining, using in vitro tissue culture assays.

#### 13.4.2.4 Elispot assays

The magnitude and breadth of HIV-1-specific CD8 T cells will be analyzed by interferon- $\gamma$  elispots, using established protocols.

### 13.4.3 Analysis of immune activation

Immune activation will be determined by proportions of CD38/HLA-DR positive CD4 and CD8 T cells. The following soluble markers of immune activation will be considered: 2D-Dimer, IL-6, hs-CRP, IP-10.

## 13.5 Gene Expression Profiling

Gene expression intensities of interferon-stimulated genes will be analyzed using PCR or microarray-based assays.

## 13.6 Immunogenetic Studies

HLA class I alleles and SNPs in the region of the IL-28B gene locus (rs12979860, rs8099917, rs12980275) will be typed in all study participants using standard protocols.

## Protocol

### 13.7 Exploratory Analyses

Other exploratory virological and immunological parameters may be analyzed, as new assays may become available. The PBMCs and serum collected for storage will be used for these exploratory assays.

## 14.0 DATA EVALUATION AND STATISTICAL ANALYSIS

### 14.1 Co-primary Endpoints

- The cumulative frequency and severity of grade  $\geq 1$  adverse events, grade  $\geq 1$  laboratory abnormality, and other serious adverse events (SAEs) during the one week treatment period.
- Changes from baseline in the reservoir of HIV-1 infected CD4 T cells, measured on a log scale using assays to evaluate CD4 T cell-associated proviral HIV-1 DNA, after completion of the combined treatment (on day 10 after study initiation) in treatment arm A vs. treatment arm B vs. treatment arm C.

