ART will be continued throughout the entire treatment course in the entire study population.

**OBJECTIVES:** The primary objectives of this study are (i) to evaluate the safety and tolerability of combined treatment with panobinostat and pegylated IFN- $\alpha$ 2a in individuals with well-controlled HIV-1 infection on suppressive cART, and (ii) to evaluate effects of combined treatment with panobinostat and pegylated IFN- $\alpha$ 2a on the reservoir of HIV-1 infected cells in comparison to effects of treatment with panobinostat only or with Interferon- $\alpha$ 2a only.

**ENDPOINTS:** The two co-primary study endpoints will be (i) the cumulative frequency and intensity of any (grade  $\geq$  1) adverse event and serious adverse event during the one week treatment

period (primary safety endpoint) and (ii) change from baseline in the number of latently infected CD4 T cells, as assessed by CD4 T cell-associated proviral HIV-1 DNA levels, after completion of study treatment (primary efficacy endpoint) in arm B vs. arm A or C.

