### 9.3.3 Treatment phase

Study entry will be defined as the day on which the first dose of study drug is administered (day=0, visit V3).

On this day, participants will have the following procedures performed:

- Perform a pregnancy test, ECG and vital signs/physical exam (including eye exam), as described in pre-treatment assessment (9.2.4).
- Review concomitant medications.
- Collect blood for baseline immunologic and virologic assays.
- Perform randomization to treatment Arm A or B or C.
- After the above procedures are completed, administer one s.c. dose of PEG-IFN- $\alpha$ 2a in patients randomized to treatment Arm B and C.
- Immediately after the first administration of PEG-IFN- $\alpha$ 2a, participants will be asked to take the first pill of panobinostat p.o., at the stage-specific dose if randomized to arm A or B.
- At 6h after administration of panobinostat, blood samples will be collected for virological, immunological and pharmacokinetic assays.
- 4-6 hours after administration of panobinostat, at the time of Cmax for panobinostat, a 12-lead ECG will be performed.
- On discharge, participants randomized to stage A or B will receive two more stage-specific panobinostat doses and will be instructed to take them in the mornings of study day 2 and day 4.

On Day 2, participants will be called by phone by one of the study investigators to discuss possible side effects. Participants will return on Day 4, six hours after administration of the third dose of panobinostat (visit V4), for collection of blood samples for virological, immunological and gene expression studies, as described in Table 1, and for an ECG. The full volume of blood to be collected on day 4 will only be collected if the most recently available hemoglobin level is  $\geq 12.0$  g/dL for men and hemoglobin  $\geq 11.0$  g/dL for women.

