## Protocol

### 9.3.4 Post-treatment observation period

Participants will return for additional collection of blood samples for virological and immunological analyses on day 10 (visit V5) and 28 (visit V6) (see Table 1). Preceding each blood collection, the hemoglobin levels determined from the visit before (visit V4 and V5, respectively) will be used to assess the participant's ability to give blood. A minimum requirement of hemoglobin  $\geq 12.0$  g/dL for men and hemoglobin  $\geq 11.0$  g/dL for women will be used.

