## 10.4 Monitoring for Adverse Events

### 10.4.1 Recording of Adverse Events

The occurrence of adverse events should be sought by non-directive questioning of the participant at each visit during the study. Adverse events also may be detected when they are volunteered by the participant during or between visits or through physical examination, laboratory test, or other assessments.

Each reported AE or SAE will be described by its duration (i.e. start and end dates), suspected relationship to the study drugs, and grade of seriousness.

At each visit, the participant will have an opportunity to spontaneously mention any new medical problems. The investigator should inquire about adverse events by asking one of the following standard questions:

“Have you had any (other) medical problems since the last visit?”

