### 10.5.2 Adverse Event Reporting Period

The study period during which all AEs and SAEs must be reported begins after informed consent is obtained and study treatment is initiated and ends 30 days following the last administration of study treatment or study discontinuation/termination, whichever is earlier. After this period, investigators should only report SAEs that are attributed prior to study treatment.

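### The co-primary safety endpoint stops after week 1, and no stated safety analysis covers day 10 and day 28 laboratory abnormalities that are not judged clinically significant

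*Combined protocol and SAP*

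**What the plan says.** **Endpoint.** Section 14.1 defines the co-primary safety endpoint as the cumulative frequency and severity of grade 1 or higher adverse events and laboratory abnormalities "and other serious adverse events (SAEs) during the one week treatment period". The schema in 3.0 agrees: any "adverse event and serious adverse event during the one week treatment" period. The limit is therefore not a slip in one section.

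**Dosing and visits.** The first panobinostat dose is on day 0. Participants receive the other two doses and are "instructed to take them in the mornings of study day 2 and day 4" (9.3.3). Peginterferon is given once, on day 0. Table 1 sets V4 at day 4, V5 at day 10 and V6 at day 28.

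**Collection and analysis.** AE and SAE reporting "ends 30 days following the last administration of study treatment or study discontinuation/termination, whichever is earlier" (10.5.2). Section 14.4.2 summarises recorded AEs and SAEs descriptively and names no window. Section 14.4.3 says the primary safety endpoints are tabulated by cohort and randomized treatment. Section 14.2 lists no safety endpoint.

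**Laboratory findings.** Section 11.7 grades abnormal results but records them as AEs only if the investigators judge them clinically significant.

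**Withdrawal from drug.** Section 12.1.2 asks participants who stop study drug to attend all later visits, then says their data count in the statistical analyses only up to the date of withdrawal.

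**Escalation.** Criteria (a) and (b) of 10.9 count related toxicity "prior to or on Day 28 after the treatment administration". Criterion (c) covers the study treatment only.

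**The concern.** Objective 4.1.1 and Hypothesis 1 ask whether the combination is safe and well tolerated. At primary level the answer comes from one week, although the schedule collects safety laboratory data for about four. Section 14.1 makes laboratory abnormalities of grade 1 or higher a component in their own right, separate from adverse events. That component has no counterpart after week 1.

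The result is uneven treatment of the same finding. A grade 1 neutropenia (Table 3: ANC 800-1000/ul, no action required) on day 4 is in the co-primary endpoint. The same value first seen on day 10, if not judged clinically significant, appears in no planned safety analysis. The other co-primary endpoint is read at that same day 10 visit.

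At stake is whether the final report shows, by dose and arm, what the later draws found, and whether participants who stopped drug for toxicity stay in the safety data.

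**Working it through.** **Step 1: visit days (Table 1 windows).**
- V4: day 4, +1, so days 4-5
- V5: day 10 ± 2, so days 8-12
- V6: day 28 ± 2, so days 26-30

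V5 is day 8 at the earliest, so neither V5 nor V6 can fall in the treatment week.

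**Step 2: post-dose safety assessments in Table 1, on-schedule dosing.**

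| Assessment | Post-dose times | Outside week 1 |
|---|---|---|
| CBC | D4, D10, D28 | 2 of 3 |
| Chemistry | D4, D10, D28 | 2 of 3 |
| Liver tests | D4, D28 | 1 of 2 |
| ECG | D0 (6h), D4 | 0 of 2 |

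**Step 3: where a finding with onset after week 1 is analysed.**

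| Finding | Co-primary (14.1) | 14.4.2 summary | Tabulation stated by cohort and arm (14.4.3) |
|---|---|---|---|
| AE or SAE in the reporting period | No | Yes | No |
| Laboratory abnormality judged clinically significant | No | Yes, as an AE | No |
| Grade ≥1 laboratory abnormality not so judged | No | No | No |

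The last row is the real gap. The general AE definition in 10.3.1 mentions abnormal laboratory findings, but 11.7 is the specific rule and makes clinical significance the condition.

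**Step 4: withdrawal from drug.** A participant stopped for toxicity after the first dose and before day 4 is asked to attend V4, V5 and V6. Under the literal cut-off in 12.1.2, none of those results would count. On schedule this can arise only in Arms A and B, because Arm C has a single dose on day 0. Planned places in A and B: (2+6) + (2+6) + (4+10) = 30 of 34. That is where the rule could apply, not how often it will.

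**Step 5: Tables 7 and 8.** P(at least 1) = 1 − (1−p)^n, and P(at least 2) subtracts n·p·(1−p)^(n−1). At p = 0.10:
- n = 8: 1 − 0.9^8 = 0.5695, and 0.1869 for at least 2 (plan: 0.57, 0.19)
- n = 18: 1 − 0.9^18 = 0.8499, and 0.5497 for at least 2 (plan: 0.85, 0.55)

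All 24 cells reproduce within 0.005. The arithmetic is right, but p is the probability of a primary safety event, so under 14.1 it is a one-week probability. Section 14.3 does not say so.

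The following is an illustration only. Let f be the share of participants with an event by day 28 who first have it in week 1. The documents do not give f. With a day 28 probability of 10%, the one-week probability is 0.10·f, and P(at least 1) becomes:
- f = 0.75: 0.46 (n=8), 0.75 (n=18)
- f = 0.50: 0.34, 0.60
- f = 0.25: 0.18, 0.37

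**Step 6: dosing that slips.** Under 10.8, "administration of study drugs will be delayed for a maximum of one week". A one-week delay could put the last dose at day 4 + 7 = day 11, after nominal V5. Holds under 11.2 have no stated maximum. Section 14.1 does not say whether the one week moves with dosing. A window ending at V6 (day 30 at the latest) would then stop before the 10.5.2 period, which could run to day 11 + 30 = day 41. This is why the fix below also takes in later events within that period.

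**The case against.** Much of the case on the other side stands.

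**Later events are not lost.** A reader might infer that the protocol fails to detect later events or to protect participants. It does not. Visits ask "Have you had any (other) medical problems since the last visit", so week-1 symptoms are still picked up at V5. AEs are collected after treatment (10.5.2), followed to resolution (10.7) and reviewed by both safety committees (10.1, 10.2) in every stage. Section 14.4.2 has no one-week limit, and its remark that the study is not powered to compare the arms suggests presentation by arm. This answers the point for AEs and SAEs, but not for laboratory abnormalities that never become AEs.

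**The windows do not contradict each other.** A reader might infer a contradiction between the one-week endpoint and the day 28 escalation rule. But 10.9(a)-(b) count related toxicity of high grade or seriousness, while 14.1 counts any grade regardless of attribution. Different purposes can justify different windows.

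**No harm can be sized.** The treatment week is 7 of the 28 days, or 25%, but that is a share of the calendar, not of risk. The absence of an escalation review after stage 3 is also no measure of harm, because no further stage follows. The protocol's median of more than 15 days to grade 3-4 thrombocytopenia (5.3.3) comes from 40 mg on another schedule. In the prior HIV study at 20 mg, platelets and neutrophils stayed within normal limits (5.4.3.1). All post-dose ECGs fall inside the endpoint.

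**12.1.2 is a separate issue.** It would exist with any window, and the event that led to withdrawal is still followed clinically. Both are true, but it bears on the same safety result and can be corrected in the same amendment.

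**Replacing the co-primary window is debatable.** A longer all-grade count gathers more background events, and a window ending at V6 matches neither 10.5.2 nor 10.9 exactly when doses are delayed. This is a good reason to add a longer window rather than substitute one.

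**Conclusion.** The point holds as a gap in reporting that should be fixed. With on-schedule dosing, 2 of 3 post-dose CBC and chemistry draws and 1 of 2 liver panels lie outside the co-primary safety endpoint. Abnormalities found there and not judged clinically significant fall under no stated safety analysis. Later AEs and SAEs do reach the descriptive summary, but no tabulation of them by cohort and arm is stated. Section 12.1.2, read literally, also removes the follow-up of participants stopped for toxicity.

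This rests on two readings: that 11.7 governs when a laboratory result becomes an AE, and that the date-of-withdrawal cut-off in 12.1.2 applies to safety analyses as well as efficacy. The text supports both, and neither is qualified elsewhere.

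The documents do not show how many events or abnormalities would fall after week 1, so no effect on counts is claimed. The endpoint carries no test and no success threshold, so no formal decision turns on it. The consequence is an incomplete safety result.

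**What to change.** 1. **14.1, or at least 14.2 and 14.4.2:** keep the one-week count. Add the same endpoint, including laboratory abnormalities of grade 1 or higher, from first dose through V6 (day 28 ± 2) or early termination from the study, plus any later events within the 10.5.2 reporting period. Tabulate by stage, arm, grade and attribution. If the addition is made at co-primary level, align 3.0.
2. **14.3:** state which window the probabilities in Tables 7 and 8 refer to. The figures themselves need no change.
3. **12.1.2:** state that safety data collected after withdrawal from the investigational drug, while the participant remains on study, count in the safety analysis.

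**Cost.** No new visit, sample or form is needed. The change does need a protocol amendment with IRB and any other applicable approval, and DAIDS registration (18.1, 18.3).

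The longer window will also bring in more unrelated low-grade events. In the prior panobinostat study, 20 of 15 + 20 = 35 AEs (57%) were unlikely to be related. That was over 8 weeks of treatment and 24 weeks of follow-up, so the share here may differ. Blood loss may add laboratory changes: Table 1 draws 60 + 57 + 87 + 99 = 303 cc from day 0 to day 10. Tabulating by attribution and keeping the one-week count limit this dilution.
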